## **9. Data security and protecting confidentiality**

All servers, PCs, and web applications include password protection. Both use technical safeguards mandated by Health Information Technology for Economic and Clinical Health Act (HITECH) of 2009 for the transmission and maintenance of protected health information (PHI) and personal health records (PHR). As noted above, this includes using two-way encryption, check sum, double-keying, message authentication, digital signature, Secure Sockets Layer (SSL), and password-protected accounts that define levels of access. The possibility of risk regarding confidentiality will be minimized by stripping all participant identifying information such as name, driver's license number, and social security number from all interview notes and electronic data files. Electronic study information will be kept on a file server that is secure, encrypted, and protected by password. Only authorized people will be allowed to see this information. Any study information that is kept on paper will be kept in a locked cabinet in a secure place. At the end of all study activities, the Chestnut Health Systems' research team will destroy all information that can identify participants.

The data security officers have also been identified for both CHS's GAIN ABS interview applications ([name]) and all of Chestnut's corporate systems ([name]). Responsibilities of the security officers include developing information technology (IT) security policies, increasing security awareness for all project staff, providing virus protection for IT resources, maintaining security patches on computing equipment, developing and implementing back up procedures, performing periodic vulnerability scanning on IT equipment, reviewing and updating firewall strategies and policies, and enhancing the physical security of IT resources.

Prior to using data for analyses, all data sets are de-identified by a) stripping all participant-identifying information such as name, driver's license number, and social security number from all interview notes and electronic data files, b) replacing participant research ID with a new randomly assigned ID (requiring multiple linkage files in hands of different people to re-identify an individual), and c) replacing dates with days from randomization to make deduction more difficult. As noted above, all staff accessing the data must complete human subject training and sign an agreement to respect the individual's privacy, not to attempt to re-identify them, and not to report out their individual answers in a way that someone else could re-identify them. Electronic study information will be kept in a file server that is secure, encrypted, and protected by password. Only authorized people will be allowed access to this information. Any study information that is kept on paper will be kept in a locked cabinet in a secure place. At the end of all study activities, the Chestnut Health Systems research team will destroy all information that can identify participants.

## **10. Statistical analysis plan**

Missing data. Participants will complete their baseline interview prior to randomization. Based on prior studies conducted by the applicants, it is expected that approximately 90% or more of the 3, 6, and 9-month post-randomization interviews will be completed. Among these completed interviews, prior studies conducted by the team indicate that less than 1% will have additional missing data on any of the core items required to test the study hypotheses. Multiple imputations will be used to replace the small amounts of missing data to allow the least biased estimate for each analysis. To further reduce potential bias, analyses will be rechecked by running them without missing data. If there are any clinically significant differences ( $d > |.2|$ ), a general latent variable framework will be used to analyze non-ignorable or systematic missing data that tests whether missing data is qualitatively different by condition.

Survival Analysis for Time to MAT Initiation and Time on Medication (Aim 1). The primary outcome is the days from randomization until the initiation of any kind of MAT. Relative to the referral only control group, the direct effects of RIMO on reducing the days from randomization to initiation of any MAT (H1a) and increasing the days on medication after initiation (H1b) will be evaluated with a Cox Regression model using IBM SPSS version 24 with random assignment to RIMO as the main predictor, as the investigators have done in earlier experiments. It will be examined after the point of randomization and after each follow-up interview. Survival analysis incorporates information about censorship (e.g., death, people who were not admitted to MAT within 9 months) and can incorporate covariates if needed. The output includes a case summary (e.g., missing data, other problems, descriptive statistics) and an evaluation of each term (e.g., beta, its standard error, Wald, its probability, the odds ratio, the 95% confidence interval for the odds ratio). The beta can also be converted to a Cohen's effect size *d*. All analyses will use an intent-to-treat approach (i.e., participants are analyzed as assigned regardless of their actual level of participation in RIMO). We will also conduct a secondary analysis of the time to MAT initiation after each RIMO checkup to understand the pattern over time as we have done with earlier experiments.

Direct Effects of RIMO on MAT (Aim 1). Relative to the referral only control group, the direct effects of RIMO on reducing dropout and receiving more total days of MAT will be evaluated using a multilevel structural equation modeling (MSEM) with mixed effects in MPlus (version 7.4). The analysis will model observations (Level 1) nested within participants (Level 2), with participants modeled as a random factor anchored on the baseline version of the dependent variable. Randomization to RIMO will be modeled as a Level 1 predictor. We will check for the need to use models that adjust for counts or zero saturation.

Direct Effects of RIMO on Secondary Outcomes of Time to Relapse, Opioid Use and Overdose (Aim 2) and Death, OUD, Health, Mental Health, and Health Care Utilization (Aim 3). Relative to the referral only control group, the direct effects of RIMO on time to first relapse (H2) will be evaluated with a survival analysis similar to Aim 1 H1. It will be examined after the point of randomization and after each follow-up interview. The direct effects of RIMO on days of opioid use (H2), opioid overdoses (H2), opioid-related fatality (H3), symptoms of OUD (H3), physical health problems (H3), mental health symptoms (H3), and the cost of health care utilization (H3) will also be evaluated using a series of MSEM with mixed effects in MPlus modeled in the same way as above. Most of the above variables are relatively continuous, but we will check for the need to use models that adjust for counts or zero saturation. For opioid-related fatality (H3), we will define the dependent variable as dichotomous in MPlus (equivalent to using logistic regression).

Indirect Effects of RIMO (Aims 2 and 3). To evaluate indirect effects, we will determine the extent to which the direct effects of RIMO on the above dependent variables are changed by of days of MAT received (H2 & H3) and/or days of opioid use (H3) using the Preacher and colleagues framework for testing mediation in MSEM with REML in MPlus. Loss of statistical significance in the path coefficient from the intervention conditions to the other outcome variables would indicate full mediation; a reduction in the path coefficient would indicate partial mediation. Change will be evaluated using MacKinnon's joint-significance testing of the path *z*-scores with a Sobel test using a standard error based on bootstrapping and criteria of  $p < .05$  on the degree of change.

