**Missing data.** Participants will complete their baseline interview prior to randomization. Based on prior studies conducted by the applicants, it is expected that approximately 90% or more of the 3, 6, and 9-month post-randomization interviews will be completed. Among these completed interviews, prior studies conducted by the team indicate that less than 1% will have additional missing data on any of the core items required to test the study hypotheses. Multiple imputations will be used to replace the small amounts of missing data to allow the least biased estimate for each analysis. To further reduce potential bias, analyses will be rechecked by running them without missing data. If there are any clinically significant differences ( $d > |.2|$ ), a general latent variable framework will be used to analyze non-ignorable or systematic missing data that tests whether missing data is qualitatively different by condition.

Table 1.1 provides a schedule of events by person. We are currently planning to start recruitment immediately and for 18 to 24 months. Follow up (and RIMO) at 3, 6, and 9 months will start at month 3 and be completed between months 30 to 36 depending on how long it takes to recruit the sample. Quality assurance checks will be done until all staff are certified and then quarterly during the study. Annual data safety monitoring reports will be done annual (discussed further below) and then main findings will be started immediately upon the completion of data collection.

	Timing	Passive Referral Control	RIMO Experimental
Screening and recruitment after overdose	Up to 1 week prior to random assignment	Yes	Yes
Informed Consent and Randomization	Point of random assignment	Yes	Yes
Provide a brochure on accessing MAT and financial assistance	Point of random assignment,	Yes	Yes
Interview, urine test and record abstraction	Enrollment, 3, 6, and 9 months post enrollment	Yes	Yes
RIMO Linkage Assistance	Enrollment, 3, 6, and 9 months post enrollment	--	Yes

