## **2. Primary and secondary objectives and outcome measures**

The primary outcome measure for the study is the GAIN-Quick Version 3 (GAIN-Q3). The GAIN-Q3 includes 4-6 symptom count screeners that are correlated .9 or more with the 11 to 43-symptom version in the full GAIN. It also has cut points with excellent (~90%) sensitivity, specificity, and area under the curve (AUC) relative to the full GAIN in 9 problem areas related to substance use disorders, physical health, internalizing and externalizing mental health disorders, as well as school, work, stress, HIV risk behaviors/victimization, and crime/violence. The days of use measures have been validated against the Timeline Follow-back, collateral reports, and urine and saliva tests. The GAIN-Q3 also includes summary measures for health care utilization, functional impairment, quality of life, and life satisfaction. The GAIN-Q3 includes the behavioral health screener and health care utilization measures that have been recommended by NIH's Phenx common data elements as two of the most reliable, valid, efficient, and inexpensive tools in the field. At each follow-up, the Q3 follow-up will be supplemented with a) a section on overdose and naloxone experiences, and b)

symptom counts from the OUD scale. Table 2.1 crosswalks the key independent measures and secondary outcomes from the hypotheses to their definitions, reliability, data sources, and the specific aims they address.

Table 2.1. Crosswalk of Variables, Definition, and Aims	H1	H2	H3
Experimental Assignment: Based on computer-generated urn randomization, participants will be assigned to the referral only control group or the experimental RIMO condition.	R	R	R
MAT Time to Initiation: Days from index naloxone administration to the initiation of any kind of MAT, from treatment records.	O		
Length of Staying on Medication: Days between MAT initiation and discharge, from treatment records.	O		
MAT Days: Total days of MAT over 9 months from GAIN-Q3 and treatment records.	O	M	M
Time to Relapse: Days from randomization to next subsequent use of opioids or heroin based on GAIN Q3 follow-up interviews and urine tests.		O	
Opioid Days of Use: Days of opioids and/or heroin use summed over the GAIN-Q3 follow-up interviews.		O	M
Opioid Overdose: Number of opioid-related overdose[s] summed over the GAIN-Q3 follow-up interviews.		O	

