### 4. Sample size and power calculation

We plan to recruit and randomize 350 participants over 24 months. There should be 99% or more power to determine the direct effect of RIMO on the primary outcome of time to MAT initiation (H1a) assuming a sample size of 350 patients, randomized into two groups of 175 each, interviews at 4 time points for the main analysis (baseline, and 3, 6, and 9 months post-randomization), our average completion rate of 94+% per follow-up wave, and a moderate to large effect size of  $d=3.0$ . This expected effect size was based on the natural log of the odds ratio ( $\text{Log}^e(\text{OR})=d$ ) of initiating MAT ( $\text{OR}=20.2$ ) from RIMO Pilot study ([name] et al., under review). For the other tests of direct effects, the effective n for power calculations in repeated measures analysis varies between a lower bound of the number of unique people per group ( $N=175$  people), and an upper bound of the number of people randomized plus the completed follow-up interviews or 668 observations per group ( $O=(175 \text{ people at intake} + \text{average of } 94\% \times 175 \text{ people} \times 3 \text{ follow-ups})$ ) as a function of the intra-class correlation coefficient (ICC) associated with the individual and the number of repeated measures (RM) per person ( $\text{effective } n'=O/(1+\text{ICC}(\text{RM}-1))$ ). In our prior studies, ICC of the other dependent

variables ranged from .13 to .34. Thus the effective n= range from 429 to 398 per group and be capable of detecting an effect size of  $d=0.2$  or more with 80% power for a two-tailed test of  $p<.05$  of effect sizes  $d=.2$  or more. For mediation analysis, the tests should also have 80%+ power for a 2-tailed test of  $p<.05$  and an indirect effect size of  $d=.2$  or more.

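### The only analysis for non-ignorable missing data is run only if imputed and complete-case results differ by d > |.2|, a trigger that does not detect non-ignorable loss and is unlikely to be met at the expected 6-10% missing per wave

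*Combined protocol and SAP*

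**What the plan says.** The missing-data paragraph in Section 10 appears with the same wording in Section 1. Missing values are multiply imputed; no imputation model is given. Then: "To further reduce potential bias, analyses will be rechecked by running them without missing data. If there are any clinically significant differences" exceeding 0.2 in absolute d are found, "a general latent variable framework will be used to analyze non-ignorable or systematic missing data". That conditional model is also the step meant to test whether missing data differ in kind between the arms. Neither section plans any other selection, pattern-mixture or tipping-point analysis.

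Section 10 expects that "approximately 90% or more of the 3, 6, and 9-month post-randomization interviews will be completed". Section 4 assumes "our average completion rate of 94+% per follow-up wave". Expected loss is therefore about 6% to 10% per wave.

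Table 2.1 in Section 2 shows which outcomes depend on the interviews. Opioid use, for example, is "Days of opioids and/or heroin use summed over the GAIN-Q3 follow-up interviews", and overdoses and costs are also sums over interviews. OUD symptoms, physical health and mental health are interview scores, time to relapse uses interviews and urine tests, and MAT days combine interviews and records. Time to MAT initiation is "Days from index naloxone administration to the initiation of any kind of MAT, from treatment records". Time on medication also comes from treatment records, and fatality from death records.

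**The concern.** Loss is non-ignorable when, given what was observed, it still depends on the value that was not seen. A person who misses the 6-month interview because of heavy current opioid use is an example. Standard imputation fills the gap from observed predictors, and the complete-case rerun drops the person. Neither uses the unseen value. The difference between the two shows how much the observed predictors explain, and it says nothing about the remainder. A small difference is therefore no reassurance, yet the plan treats it as one.

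The threshold is also coarse. It equals the d=0.2 for which Section 4 sizes the non-primary direct-effect tests and, with "For mediation analysis, the tests should also have 80%+ power for a 2-tailed test of" the same effect size, the mediation tests. A gap just short of the target effect would prompt nothing.

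Loss that differs by arm is plausible. RIMO participants have Linkage Manager contact for at least 4 weeks and checkups at 3, 6 and 9 months, and controls do not. The tracking procedures cover both arms, which helps but does not equalise contact. If loss depends on unseen opioid use and differs by arm, the estimated effects on opioid days, overdoses, symptoms and costs, and the mediation paths through MAT days and opioid days, could be biased without any planned analysis showing it. The direction depends on which arm loses its worse participants.

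**Working it through.** **1. The plan's own figures.** Observations per group at 94% completion: 175 + 0.94 × 175 × 3 = 668.5, stated as 668. For d=0.2, 80% power and two-sided .05, n per group = 2 × (1.960 + 0.842)² / 0.2² = 393. The stated effective n of 398 gives 80.5% power. So 0.2 is the smallest effect these tests are sized for.

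**2. What the trigger requires.** In each arm, imputed minus complete-case mean = f × (mean of imputed values − mean of observed values), where f is the fraction missing. With equal f by arm, the gap in d is f × the between-arm contrast in that shift, so the contrast needed is 0.2/f.

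| Situation | f | Contrast needed (SD) |
|---|---|---|
| One wave, 94% complete | 0.06 | 3.33 |
| One wave, 90% complete | 0.10 | 2.00 |
| Three-wave sum, 94% per wave | 1 − 0.94³ = 0.169 | 1.18 |
| Three-wave sum, 90% per wave | 1 − 0.90³ = 0.271 | 0.74 |

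The last two rows assume that waves are lost independently.

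**3. Why the gap measures the wrong thing.** Suppose loss depends on the outcome, imputation uses a baseline value correlated r with it, and arms are compared without adjustment. To a first approximation imputation recovers r² of the complete-case bias and leaves 1 − r². So gap ≈ r² × (complete-case bias), and a gap of 0.2 needs a complete-case bias of 0.2/r²: 0.80 at r=.5, leaving 0.75 × 0.80 = 0.60 in the imputed result, or 0.41 at r=.7, leaving 0.51 × 0.41 = 0.21. The weaker the predictors, the more bias remains and the less likely the trigger is to fire.

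**4. Simulation, unadjusted comparison.** 175 per arm, true d=0.2, arm-specific imputation on baseline, 20 imputations, 300 trials per setting, logistic loss with an assumed slope of 2 per SD, acting in opposite directions by arm, 10% missing.
- Loss driven by the unseen outcome, r=.5: bias −0.22 imputed and −0.29 complete-case, mean gap 0.06, trigger fired in 0%.
- Loss driven by baseline (ignorable), r=.7: imputed bias 0.00, trigger fired in 50%. A separate simulation of this pattern gave 32%.

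The trigger stays silent in the first case, where the model is needed, and can fire in the second, where it is not.

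**5. Simulation, one wave, baseline-adjusted.** Section 10 anchors its models on the baseline value. Settings: 175 per arm, no true effect, 20 imputations from baseline and arm, r=.34 or .7, 16 scenarios × 600 trials. The largest gap was 0.027 and the trigger fired in 0 of 9,600 trials. When only controls lost worse cases (a shift of about 1.3-1.4 SD), bias at r=.34 and .7 was 0.069 and 0.041 at 6% missing, and 0.121 and 0.072 at 10%, equal in the imputed and complete-case analyses. With the same mechanism in both arms, bias was about 0.

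**6. Simulation, three-wave sum.** Section 4 says that ICCs of the other dependent "variables ranged from .13 to .34". These were used as the between-wave correlation, with 200 trials per scenario.

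| Loss per wave, ICC | Control-only: bias, fired | Opposite by arm (extreme): bias, fired |
|---|---|---|
| 6%, .13 | 0.116, 0% | 0.227, 0% |
| 6%, .34 | 0.083, 0% | 0.172, 0% |
| 10%, .13 | 0.199, 0% | 0.401, 1.5% |
| 10%, .34 | 0.151, 1.0% | 0.303, 10.0% |

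**The case against.** **The scale of d is not fixed.** Section 4 converts with log(OR)=d, while Section 10 mentions Cohen's d. If 0.2 is a log-odds difference, it is about 0.2/1.81 = 0.11 SD, and the per-wave contrasts needed fall to about 1.1 SD at 10% missing and 1.8 SD at 6%. For three-wave sums (assumed loss slope 1.5 per SD), a 0.11 SD trigger fired at 10% loss per wave in 21% of trials (control-only) and 76% (opposite loss) at ICC .34, and in 11% and 28% at ICC .13. At 6% it fired in 0-33%. This stands for sums. It does not rescue the baseline-adjusted per-wave analysis, where the largest gap of 0.027 is far below 0.11.

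**Strong predictors open the gate.** In the unadjusted simulation with r=.7 and strong opposite outcome-related loss, the trigger fired in 54% of trials at 18% missing and 95% at 27%. With r of .5 or less it fired in at most 5%, and with loss in one arm only in at most 11%. At the plan's ICCs, the baseline value correlates with a three-wave sum by 3ρ/√(3+6ρ): 0.20 at ρ=.13 and 0.45 at ρ=.34. So r=.7 is outside the planned range.

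**The harm is modest.** Single-wave control-only bias is 0.04-0.12, bias vanishes when both arms lose alike, and nothing in the plan points to opposite loss by arm. Intensive tracking and phone, jail and hospital interviews keep loss low, and the record-based primary outcome is largely untouched. All of this stands and limits the severity. Still, 0.07-0.12 at 10% missing is 35-60% of the 0.2 target.

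**The simulations are simplified.** Section 10 models observations within participants, so the biases for sums rest on one reading of Table 2.1. Record abstraction at each wave could improve an imputation model that is not specified. Time to relapse was not simulated. These are fair limits on the numbers, but they leave the reasoning in step 3 unchanged.

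**Conclusion.** The concern holds. The only planned non-ignorable analysis depends on a comparison that cannot detect non-ignorable loss, and that conclusion needs no simulation. That the trigger is unlikely to be met is well supported for baseline-adjusted per-wave analyses at 6-10% missing. It is less certain for three-wave sums, especially if d is on the log-odds scale.

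The size of the bias is illustrative because the loss mechanism is assumed: roughly the missing fraction times the differential shift between arms. Shifts of 0.5 to 1.5 SD give 0.03-0.09 at 6% and 0.05-0.15 at 10%. The scope is the interview-based outcomes and mediators. MAT initiation, time on medication and fatality are largely unaffected. This should be corrected, but it does not threaten the primary analysis.

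**What to change.** In Sections 1 and 10, delete the d > |.2| condition and commit to a non-ignorable sensitivity analysis for every interview-based outcome and mediator. One option is an arm-specific delta-adjusted (pattern-mixture) analysis on the existing imputations, reporting the shift at which the conclusion changes. The latent-variable model already named can serve instead, provided it is run unconditionally. Keep the complete-case rerun as a description only.

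The cost is one more planned analysis to run and report, with no new data. Specifying it now also avoids choosing a method after the results are seen.

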In Phase 1 (R21), the study team worked with the CFD to train Emergency Medical Service (EMS) teams to obtain authorization for release of contact information from individuals after an overdose reversal. The experimental pilot study tested the feasibility of each step in the intervention protocol and compared individuals who were randomly assigned to receive either a treatment referral pamphlet or the RIMO intervention on treatment received at 30-day follow-up. Qualitative data was also obtained from a focus group with participants in the RIMO group. A total of 75 individuals who had received naloxone from EMS were informed about the study; 50 (67%) of these signed the authorization form and provided their contact information; 33 met with the study team, consented to participate, and were randomized. Compared to the control group, the RIMO group (n=16) had higher odds of receiving any treatment for opioid use (OD = 7.94) and any MAT (OR = 20.2); they received significantly more days of opioid treatment (15.2 vs. 3.4) and more days of MAT (11.2 vs. 0.76) relative to the control group (n=17; all p < .05). Qualitative data highlighted the core components of the RIMO intervention. The pilot study demonstrates the feasibility of partnering with EMS and using the RIMO intervention to address the challenges of linking and engaging individuals into MAT after opioid overdose. These findings have been submitted for publication ([name] et al., under review) and were used to refine the study design for phase 2.

In Phase 2 (R33), research staff will continue to work with the CFD's EMS division and CPD to identify people who have just had an opioid overdose reversed with naloxone, recruit them into the trial, randomize them to a passive referral (via a brochure) vs. the RIMO experimental group. Using the study recruitment and RIMO procedures refined in Phase 1, a total of 350 individuals will be recruited and randomly assigned to the "referral to MAT" control or to "RIMO". All participants will receive standardized assessments at baseline and 3, 6, and 9 months post-randomization. The study's aims and their associated hypotheses are:

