**Aim 1: Evaluate RIMO's direct effect on linkage to MAT, length of time on MAT, dropout, and total days of MAT.**

H1: Relative to the control group, RIMO will have a direct effect on: a) initiating MAT sooner, b) staying on medication longer, c) reducing dropout, and d) receiving more total days of MAT.

**Aim 2: Evaluate RIMO's direct and indirect (via MAT) effects on time to relapse, opioid use, and opioid-related overdose.**

H2: RIMO will have direct and indirect (via days of MAT treatment) effects on: a) time to relapse, b) days of opioid use, and c) number of overdoses.

**Aim 3: RIMO's direct and indirect (via MAT and opioid use) effects on opioid-related fatalities, OUD symptoms, physical health, mental health and the cost of health care utilization.**

H3: RIMO will have direct and indirect (via days of MAT treatment and days of opioid use) effects on: a) opioid-related fatalities, b) opioid use disorders symptoms, c) physical health, d) mental health, and e) cost of health care utilization.

Referral Only Control. During the phase 1 pilot, we collaborated with our study partners as well as the Illinois Opioid STR partners to develop a brochure that includes a list of MAT providers in Chicago, and their location, telephone number, hours of operation, adjacent bus lines, and type of funding accepted (e.g., Medicaid). In addition, the brochure includes a range of other SUD treatment options (e.g., residential or outpatient drug-free treatment), including office-based physicians who prescribe buprenorphine or other forms of MAT. This brochure is will be given to participants in both groups at the baseline assessment. Research staff will follow a script that does not include any statements regarding motivation for treatment. At present, based on our interviews with key informants and focus group with pilot study participants, there is currently no systematic method in place for referring individuals to MAT (or other SUD treatment) either from the first responders following administration of naloxone or at the EDs following their admission for opioid-related overdose. Hence, this condition represents more than the “usual care” in the community.

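### H1b compares time on medication among MAT starters only, so its result is not a randomized effect of RIMO

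*Combined protocol and SAP*

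**What the plan says.** Aim 1 in Section 1 lists four direct effects of RIMO: earlier initiation (H1a), then "b) staying on medication longer, c) reducing dropout, and d) receiving more total days of MAT".

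Table 2.1 in Section 2 defines the H1b outcome as "Days between MAT initiation and discharge, from treatment records". In Section 10, the survival analysis paragraph says that "increasing the days on medication after initiation (H1b) will be evaluated with a Cox Regression model", with random assignment as the main predictor, and groups this with H1a as a direct effect of RIMO. Its examples of censoring include people not admitted to MAT within 9 months. It defines intent-to-treat by reference to participation in RIMO, and allows covariates if needed.

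A separate multilevel model in Section 10 covers "the direct effects of RIMO on reducing dropout and receiving more total days of MAT" (H1c and H1d). Table 2.1 defines the H1d measure as "Total days of MAT over 9 months from GAIN-Q3 and treatment records". Dropout has no row in Table 2.1 and no stated denominator.

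Section 4 gives H1a its own power statement. It then continues "For the other tests of direct effects, the effective n for power calculations in repeated measures analysis" and claims 80% power at d=0.2 from an effective n of 429 to 398 per group. No power statement names H1b.

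**The concern.** Time from initiation to discharge does not exist for someone who never starts MAT. The H1b model therefore conditions on an event after randomization that RIMO is designed to change. If H1a succeeds, the RIMO starters will include people who would not have started unaided, and the control starters will not. Randomization does not balance these two groups.

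The hazard ratio then carries selection as well as any effect on retention. If people linked by RIMO stay on medication less long than people who start unaided, an effective RIMO can look neutral or harmful. If they stay longer, a retention benefit can appear where there is none. If both kinds of starter stay equally long, there is no bias. The plan does not acknowledge the conditioning or plan a sensitivity analysis for it, yet it attributes the result to RIMO.

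**Working it through.** **1. Who enters the model.** The SAP never says that H1b is limited to starters; this follows from the outcome definition. Censoring people not admitted within 9 months works for H1a, where time runs from randomization. In H1b such a person would be censored at time zero and contribute nothing to the Cox partial likelihood.

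**2. Whether the arms' starters should differ.** Linkage Managers re-contact people who refuse, in order to convert them (Sections 1 and 8). The pilot, which compared the groups "on treatment received at 30-day follow-up", gave an odds ratio of 20.2 for any MAT, and Section 4 plans H1a on it.

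**3. The plan's power figure.** Observations per group: 175 + 0.94 × 175 × 3 = 668.5 (stated as 668). Taking the stated effective n as given, two-sided power at d=0.2 is 80.5% for 398 and 83.4% for 429, so the 80% claim follows from those n. (The stated formula with ICC .13 to .34 gives 481 to 331 for four measures and 531 to 398 for three. The 429 is not reached either way, but this point does not depend on it.) An effective n built from repeated observations does not apply to one duration per starter.

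**4. Starting rates (assumed).** If the pilot odds ratios are unadjusted, the only tables with 16 vs 17 participants that match them are 13/16 vs 3/17 for any MAT, (13/3)/(3/14) = 20.22, and 13/16 vs 6/17 for any treatment, (13/3)/(6/11) = 7.94. That gives 81% vs 18% on MAT by 30 days. The gap may be smaller by 9 months, so 60% vs 30% and 55% vs 40% were also used.

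**5. Power among starters.** With n1 and n0 starters of 175 per arm, δ = 0.2 × √(n1·n0/(n1+n0)) and power = Φ(δ−1.96) + Φ(−δ−1.96). For 142 vs 31, δ = 0.2 × √(4402/173) = 1.01. As an event-based check, Schoenfeld's formula was applied at a hazard ratio of 0.8. It assumes exponential discharge with a 90-day median and censoring at 240 days, so 1 − 2^(−240/90) = 84% of starters are discharged.

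| Starting, RIMO vs control | Starters | Power, d=0.2 | Detectable d (80%) | Discharges | Power, HR 0.8 | Detectable HR (80%) |
|---|---|---|---|---|---|---|
| 81% vs 18% | 142 vs 31 | 17% | 0.56 | 146 | 18% | 0.55 |
| 60% vs 30% | 105 vs 52 | 22% | 0.48 | 132 | 23% | 0.60 |
| 55% vs 40% | 96 vs 70 | 25% | 0.44 | 140 | 26% | 0.62 |

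Even if all 175 per arm started, power at d=0.2 would be 46%.

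**6. Size of the bias.** The simulation ran 2,000 trials of 175 per arm per scenario, with no effect of RIMO on discharge. An unmeasured trait changed the log-odds of starting by 1 to 1.5 per SD and the log-hazard of discharge by 0.3 to 0.5 per SD. Discharge and censoring were as in step 5, and a Cox model was fitted among starters. All these settings are assumptions. In the first direction, people more inclined to start also stay longer; in the second, they stay less long. All four combinations of coefficients were run for the first direction, and the two extremes for the second.

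| Starting | HR, selection against RIMO | Significant harm | HR, sign reversed | Significant benefit |
|---|---|---|---|---|
| 81% vs 18% | 1.17–1.40 | 10–27% | 0.72–0.84 | 14–36% |
| 60% vs 30% | 1.07–1.17 | 6–12% | 0.85–0.93 | 7–14% |
| 55% vs 40% | 1.04–1.08 | 4–6% | 0.93–0.97 | 4–7% |

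The nominal rate in each direction is 2.5%. Without selection the model gave HR 1.00 and 2.1–2.2% significant harm.

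**7. Direction.** Pilot MAT days per inferred starter are 11.2 × 16/13 = 13.8 for RIMO and 0.76 × 17/3 = 4.3 for control. This favors RIMO, but earlier starting within the 30-day window would also produce it, so it does not settle the sign.

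**8. Dropout (H1c).** Never-starters cannot drop out. If dropout were counted over everyone randomized, with equal dropout among starters, the RIMO:control dropout ratio would equal the initiation ratio: 4.6, 2.0 and 1.4 in the three scenarios. If it were counted among starters, it would have the H1b problem.

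**The case against.** The strongest reply is that little rides on H1b. The single primary outcome, H1a, covers everyone randomized. H1d is an all-randomized measure of MAT exposure, and Section 10 already plans to check for zero saturation. H1b is not called confirmatory, and the stopping rules in Sections 20 and 23 do not name it. The conditioning is visible in its definition, and the plan uses direct mainly in contrast to indirect, mediated effects. This all stands and limits the seriousness of the point. It does not remove it, because the plan still attributes the H1b contrast to RIMO.

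The size of the bias is also assumed. The 81% vs 18% scenario applies inferred 30-day counts from 33 people to a 9-month trial, and at 55% vs 40% the distortion is small. The simulation gives no credit for covariate adjustment. Adjustment for baseline severity might reduce the bias, but could not be relied on to remove it.

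On power, Section 4 can be read as never covering the H1b Cox model, in which case H1b has no power statement. Most of the shortfall comes from having one value per person (46% even if everyone starts), not from selection. Both are fair, and neither makes the 80% figure apply to H1b.

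Finally, the dropout ratios only restate assumed initiation ratios, under a definition the plan does not give. They show why a denominator is needed, not what the trial would find.

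**Conclusion.** The point holds. As defined, H1b is a comparison among MAT starters, and neither the intent-to-treat sentence nor optional covariates restores the randomized comparison. That conclusion rests on the plan's own definitions and is firm.

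The size is much less certain. It depends on assumed starting rates, selection strength, discharge distribution and censoring time, and the sign is unknown. The distortion ranges from minor when starting rates are close to substantial when they are far apart as in the pilot, and it vanishes if both kinds of starter stay equally long. Power at d=0.2 is low throughout: 17% to 25% among starters in the scenarios used.

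This should be fixed before analysis, but it does not threaten the primary outcome or H1d. The missing dropout definition is a related, smaller gap.

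**What to change.** - Rest any conclusion about retention on a measure that keeps everyone randomized. One choice is H1d total MAT days, stating that non-starters count as zero. Another is being on MAT at 3, 6 and 9 months, with non-starters counted as not on MAT.
- Keep the H1b Cox model, but label it in Section 10 as a descriptive, non-randomized comparison among starters. Report the number of starters and their baseline characteristics by arm beside it.
- State in Section 4 that the 80% power claim does not cover H1b.
- Add a row to Table 2.1 that defines dropout and its denominator. Report dropout among starters as descriptive, like H1b.

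The cost is SAP wording and one table row; all the data are already planned. The drawback is that an all-randomized measure combines starting with staying. It does not isolate retention, and it partly overlaps H1a and H1d. The narrower question of how long starters stay would still be answered only descriptively.
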